All CT scans performed for pulmonary nodule surveillance should be done using low radiation-dose technique, however, this vitally important aspect of imaging quality and safety is often overlooked during CT surveillance of lung nodules. Guidance on low radiation-dose techniques will be provided to each site and the study protocol will strongly recommend the use of these or equivalent low radiation-dose protocols for all follow up CT scans. During the first 3 months of the trial, site project coordinators will review the CT examinations and record radiation dose metrics (CT Volumetric Dose Index [CTDI vol] and Dose Length Product [DLP]) on a large sample of chest CTs performed at their site (10-50% depending on population; 100% for California hospitals as these data are included in the medical record by law) to determine if the

CTs were performed using appropriate techniques. Staff will be trained in radiation dose extraction techniques. Radiation dose metrics will be calculated monthly by site, provided to the Data Coordinating Center, and reviewed during regular meetings. Initiatives to ensure compliance with low-dose examinations will include site visits and radiology-specific lectures.

Table 4: Definition and Source Information for Outcomes, by Specific Aim				
Aim	At Risk	Outcome	Definition	Source
1	Participants with cancerous nodules	AJCC 7 th edition Stage >T1a or AJCC 8 th edition stage >T1b	Tumor size >20 mm at time of resection or radiotherapy.	Cancer Registry, EHR
		Time to diagnosis and treatment	Time to diagnosis and time to treatment with surgery, radiotherapy or chemotherapy, measured from date of index CT scan to date of first treatment.	
		Survival	Measured from date of index CT scan to death or censoring.	
2	All patients with nodules and access to email	Nodule-related distress	Measured with validated IES-R. Assessments performed 1-2 months after index CT scan, at 13-24 months, and at end of follow-up.	Self-administered web survey
		Anxiety	Measured with validated STAI-6. Assessments performed 1-2 months after index CT scan, at 13-24 months, and at end of follow-up.	
		General health status	Assessments performed 1-2 months after index CT scan, at 13-24 months, and at end of follow-up.	
		Satisfaction with evaluation	Measured with novel items, Likert-type scale. Assessment performed at 13-24 months and at the end of follow-up	

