H1a: Among participants with nodules that prove to be cancerous, less intensive surveillance will be non-inferior to more intensive surveillance for: (a) the frequency of cancer progression beyond AJCC 7th edition stage T1a disease (or T1b for AJCC 8th edition) and (b) the frequency of cancer progression beyond AJCC 7th edition TNM stage T1aN0M0 (or T1bN0M0 for AJCC 8th edition). In addition, among participants with *lung nodules*, less intensive surveillance will be non-inferior to more intensive surveillance for: (a) the frequency of cancer progression beyond AJCC 7th edition stage T1a disease (or T1b for AJCC 8th edition); and (b) the frequency of cancer progression beyond AJCC 7th edition TNM stage T1aN0M0 (or T1bN0M0 for AJCC 8th edition).. Furthermore, in exploratory analyses for HTE, we hypothesize that individuals who are most likely to benefit from more intensive surveillance will include older people, people with larger nodules (>8 mm), patients with solid or part-solid nodules (compared with non-solid

nodules), and individuals with nodules detected by screening (compared with individuals who have nodules that are incidentally detected).

H1b: Among participants with nodules that prove to be cancerous, more intensive surveillance will result in more timely diagnosis than less intensive surveillance.

H1c: Among participants with nodules that prove to be cancerous, less intensive surveillance will be non-inferior to more intensive surveillance for overall survival. Among participants with lung nodules, less intensive surveillance will be non-inferior to more intensive surveillance for overall survival.

H2a: Among all participants with a lung nodule ≤ 15 mm, more intensive surveillance will be associated with greater levels of emotional distress and state anxiety at 13-24 months, but levels of distress and anxiety similar to less intensive surveillance at 1-2 months and ≥ 25 months.

H2b: Among all participants with a lung nodule ≤ 15 mm, more intensive surveillance will be associated with scores similar to less intensive surveillance for general health status at 1-2 months, 13-24 months and ≥ 25 months.

H2c: Among participating radiologists and pulmonologists, satisfaction with the surveillance protocol will be greater among those who practice at institutions assigned to the less intensive protocol.

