Patient surveys: To examine whether among all participants with a lung nodule ≤ 15 mm, more intensive surveillance will be associated with greater levels of emotional distress and state anxiety at 13-24 months, but levels of distress and anxiety similar to less intensive surveillance at 1-2 months and ≥ 25 months, comparisons of the levels of emotional distress and state anxiety (measured according to the scoring systems detailed in Table 4) will be assessed at 1-2, 13-24, and ≥ 25 months from the first CT scan, respectively, again using a hierarchical model to capture site-to-site variability. At each time point, we will compare the levels between surveillance groups via a mixed effects model, where site will be considered as random effects to account for within-cluster correlations. Formal tests of both between-site and between-subject heterogeneity will be used to rule out sources of clustering that are not warranted. Structural Equation Models will be used to compare levels of distress and anxiety at 13 months, using second-order factors when valid subscales exist, to assess whether accounting for measurement error in the survey items changes our conclusions. Finally, we will use Latent Class Regression (LCR) to identify subgroups of the study population whose change in levels of emotional distress and state anxiety may differ, since LCR allows for modeling of time trends along with adjustment demographic and clinical characteristics within an arbitrary number of latent classes.⁶² For example, there could be the following three classes: 1) patients whose

levels are elevated at 1-2 months after being notified of a nodule, but then drop off and stay low throughout follow-up; 2) patients whose levels are elevated at 1-2 months and stay high throughout follow-up; 3) and patients whose levels are normal at 1-2 months following surveillance, and then increase during follow-up. The differences in changes of levels of distress and anxiety between the latent classes over time would then be assessed by including a piecewise linear function of time in the LCR model, as described above.

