We will continue recruitment through the end of the study to collect additional data for HTE analyses with greater statistical power for Aim 1. We assume 10% loss to follow-up before final diagnosis is established based on KPSC membership data. This yields an estimated sample size for analyses of 960 individuals with cancerous nodules for Aim 1, and 32,000 individuals with small nodules for Aims 2-4.

Aim 1: For the primary outcome, the baseline risk of progression has not been reported. Conservatively, we assume that 5% of patients will progress from a tumor ≤ 15 mm to a tumor > 20 mm during the surveillance period. Assuming a two-sided alpha of 0.05, and an intraclass correlation coefficient (ICC) of 0.01, a sample size of 888 unique patients with cancerous lung nodules (444 per arm) is required to achieve 83% power to detect an absolute increase in tumor progression of 5 percentage points. Thus, our anticipated sample size of 960 unique patients with cancerous lung nodules provides adequate power to show non-inferiority of the less intensive surveillance strategy for our primary outcome of lung cancer stage $> T1a$ at diagnosis. The most uncertainty in our assumptions is for the ICC. We will have at least 80% power to detect a 5% increase in our primary outcome for ICC values of 0.012 or less. At the baseline ICC value of 0.01, a total sample size of 32,560 enrolled (including 888 patients with cancerous nodules) will have 0.83 power; for an ICC value of 0.012, a total sample size of 35,200 enrolled (960 patients with cancer) will also have 0.83 power.

Aim 2: Prior studies of anxiety and distress in lung cancer screening have shown that the identification of a lung nodule leads to anxiety and emotional distress that subsequently dissipates over 1-2 years.^{56 63 52} For our analyses of anxiety and emotional distress, we will have $> 90\%$ power to detect an effect size of 0.22 standard deviation, assuming an ICC of 0.01, even if the response rate is as low as 5%, resulting in an estimated sample size of approximately 792 respondents in each arm.

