Subgroup Analyses/Heterogeneity of Treatment Effect: During the 7.5-year study period, we will have sufficient power to achieve our primary aims based on the planned 28 months of enrollment. We limited the period of enrollment to enable follow-up of all enrolled patients for at least 2 years, to reliably exclude a diagnosis of cancer when absent, and to assess cancer outcomes when present. Analyses will include whether outcomes vary by CT indication (lung cancer screening or unrelated to lung cancer screening), lung cancer risk factors (primarily smoking history), nodule density (solid, part-solid or non-solid), health care setting, demographic characteristics, and geographic region. Each of these subgroup analyses will be guided by the clinically plausible, pre-specified hypothesis that more intensive surveillance is more effective in subgroups that are at higher risk for more aggressive forms of lung cancer, such as older individuals; smokers and former smokers; patients with screening-detected nodules, solid nodules, or nodules of larger size; and patients from regions where a large portion of nodules are caused by endemic fungal infections.

To examine differences in “treatment” effect, we will include relevant interaction terms in all regression models, and report magnitudes of effects and standard errors for each subgroup level when interactions are statistically significant.

[figure not shown]
Missing Data: Two types of missing data might occur: (1) core study variables (such as potential confounders) may be missing for some patients because of incomplete capture in the

EHR, and (2) patients might disenroll from a health system and/or leave the capture area. We will minimize missingness of core study variables through intensive quality assurance. The Data Coordinating Center will review monthly reports for potential data issues and follow-up with site coordinators and programmers to abstract missing data, correct data issues, and document in the study database when missing data cannot be found.

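### Survey non-response is not treated as missing data, so the Aim 2 primary comparison (H2a) rests on responders with no stated protection against response that differs by arm

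*Combined protocol and SAP*

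**What the plan says.** All references are to the combined protocol and SAP.

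- **Hypothesis.** Distress and anxiety are listed as Aim 2 primary endpoints. The hypothesis is stated for the whole enrolled population: "H2a: Among all participants with a lung nodule ≤ 15 mm, more intensive surveillance will be associated with greater levels of emotional distress". It covers state anxiety as well, predicts a difference at 13-24 months, and predicts similar levels at 1-2 months and from 25 months on.
- **Power (Sample size and power calculations, Aim 2).** The plan claims above 90% power for a difference of 0.22 SD with an ICC of 0.01. The claim is said to hold "even if the response rate is as low as 5" per cent, which the plan translates into about 792 people answering per arm.
- **Model (Analysis Plan, H2a).** "At each time point, we will compare the levels between surveillance groups via a mixed effects model", with site as a random effect. Demographic and clinical adjustment is mentioned in that paragraph only for the latent class regression.
- **Adjustment elsewhere.** The H2b paragraph says its mixed models are adjusted for age, gender, ethnicity/race, smoking, BMI, nodule size and the facility-level factors balanced at randomisation. The Abstract says in general terms that the hierarchical models adjust for residual imbalance.
- **Missing Data.** "Two types of missing data might occur": core variables not captured in the EHR, and patients who disenrol or leave the capture area. Multiple imputation is planned, with missingness at random justified by information not documented in the EHR. Patients with and without missing data will be compared. The one sensitivity analysis for missing outcomes concerns lung cancers in patients who disenrol.
- **Who is surveyed.** Table 4 gives the Aim 2 population as "All patients with nodules and access to email". The Aim 2 approach, the text around Table 5 and Sources of Materials also allow regular mail.

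**The concern.** At the response rate the power statement allows, up to 95% of a primary endpoint would be unobserved. The Missing Data section expects at most 10% loss to follow-up and reasons only about EHR gaps, so nothing in it is built for missingness on the survey scale. A model fitted to whoever answers each round estimates a difference among responders. Randomisation balances those enrolled, not those who reply.

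Differential response is plausible here for three reasons:

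- Patients and providers know the assigned protocol.
- The arms give different messages. For small incidental solid nodules, Group A schedules follow-up CT in size ranges where Group B schedules none or makes it optional (Tables 2 and 3).
- The method of notification varies across sites.

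The first survey comes 1-2 months after the index CT, so there is no score from before the recommendation with which to check selection. An arm difference in who replies could create, hide or reverse a difference in distress.

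**Working it through.** **1. The plan's own figure.** Inputs are 35,200 enrolled, 10% loss, 5% response, 24 randomised units, ICC 0.01 and effect 0.22 SD. The Aim 2 text gives no alpha, so I take the Aim 1 value ("Assuming a two-sided alpha of 0.05").

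- Respondents per arm: 35,200 × 0.90 × 0.05 / 2 = 792. This matches.
- Mean cluster size: 1,584 / 24 = 66. Design effect: 1 + 65 × 0.01 = 1.65. Effective n: 792 / 1.65 = 480 per arm.
- SE = √(2 × 1.65 / 792) = 0.0645 SD. Power = Φ(0.22/0.0645 − 1.96) = 0.926. With a t reference on 22 df it is 0.90.

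The stated power reproduces with equal cluster sizes. It covers sampling error only.

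**2. How non-response enters.** With response rate r, the responder mean differs from the full-population mean by (1 − r) × gap, where gap is the responder mean minus the non-responder mean. With equal r in both arms, the bias in the arm difference is (1 − r) × (gap in A − gap in B). At r = 0.05, a between-arm difference in gaps of 0.22 / 0.95 = 0.232 SD produces a bias equal to the target effect. If the gaps are equal, the bias is zero.

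**3. Illustration (selection strength assumed; the documents give no figure).** Let distress x be standard normal. In one arm the response probability is p(x) = 1/(1 + exp(−(a + bx))), with b = ln(odds ratio per SD) and a set so that mean response is r. In the other arm response does not depend on x. The bias is E[x·p(x)]/r:

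| Odds ratio per SD | r = 5% | r = 20% | r = 30% |
|---|---|---|---|
| 1.1 | 0.09 SD | 0.08 SD | 0.07 SD |
| 1.3 | 0.25 SD | 0.21 SD | 0.18 SD |

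The problem shrinks as response rises but does not depend on the 5% floor.

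**4. Precision of a weighted estimate at 792 per arm.** A weight CV of 0.5 (assumed) gives a variance factor of 1 + 0.5² = 1.25.

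- Applied to the within-site part only: design effect about 1.65 + 0.25 = 1.90, SE = √(2 × 1.90 / 792) = 0.0693, power 0.89.
- Applied to all the variance: 1.65 × 1.25 = 2.06, SE 0.0722, power 0.86.
- With a weight CV of 1.0 (factor 2), the same two calculations give 0.77 and 0.67.

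**The case against.** The strongest reply is that the plan is less bare than it looks.

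- **Adjustment.** A reader might infer that H2a is unadjusted. The documents do not establish that. H2a uses a mixed model, the H2b paragraph says its mixed models will be adjusted, and the Abstract promises adjustment generally. What stands is that adjustment for H2a is unspecified.
- **Imputation.** Multiple imputation and a comparison of patients with and without missing data are planned. Both are generic and rest on EHR gaps. No imputation model for the surveys is given, so neither clearly reaches non-response.
- **Email.** A reader might infer that patients without email are excluded. Table 4 says so, but several other sections allow mail. This is an inconsistency, not a settled restriction.
- **Arm-specific contact.** A reader might infer that every organisation contacts patients for one arm only. Kaiser Permanente Southern California has service areas in both arms. The enrolment section also mentions centralised survey distribution, and letter timing was a balancing factor at randomisation. These weaken the case for differential response without removing it.
- **Size.** The 5% is a worst case for power. The bias figures assume selection on distress itself in one arm only, for which the documents offer no evidence, and weights from EHR variables would remove only the part those variables explain. This objection stands. It is why weighting belongs in a sensitivity analysis and needs a not-at-random analysis beside it.

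**Conclusion.** The gap is real and worth closing. For a primary Aim 2 endpoint, survey non-response is not named as missing data, the covariates for H2a are not specified, and no weighting or departure from missing at random is planned for the surveys. As written, the comparison is one of responders, with no stated protection against response that differs by arm.

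The possible size is about 0.09 to 0.25 SD at 5% response under the one-arm selection assumed above, against a target of 0.22 SD. It is zero if selection is the same in both arms. These figures show sensitivity; they are not an estimate of actual bias. The documents do not support the stronger conclusions that the Aim 2 result will be biased or that its power statement is wrong.

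**What to change.** 1. **H2a paragraph.** Adjust the mixed models for the covariates already listed for H2b: age, gender, race/ethnicity, smoking, BMI, nodule size and the facility-level balancing factors. State whether the target is all participants or responders, and whether multiple imputation covers the surveys.
2. **Missing Data section.** Name survey non-response as a third type. Report response rates and responder characteristics by arm and round.
3. **Weighted sensitivity analysis.** For each round, model response among all enrolled, living participants who have not opted out, with arm-by-covariate terms. Do not put fixed site effects beside arm: each randomised unit belongs to one arm, so arm could not then be estimated separately. Use stabilised, truncated inverse-probability-of-response weights. Include pre-index anxiety or depression only if it can be extracted; it is described for the preliminary cohort but not named among the trial's variables.
4. **Not-at-random sensitivity analysis.** Vary the responder/non-responder gap separately by arm and show how large a difference in gaps would change the conclusion. Weights correct only for measured variables.
5. **Table 4.** Reconcile the email-only population with the mail option in the other sections.

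**Cost.** Some analysis work, and no new patient contact. The primary analysis keeps all respondents and loses no precision to weighting. The weighted estimate is less precise: at 792 per arm, power is about 0.86 to 0.89 instead of 0.93 with a weight factor of 1.25, and lower with more variable weights. Making it primary would be a trade-off, which is why it is proposed as a sensitivity analysis.

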4	I felt irritable and angry.	Not at all	A little bit	Moderately	Quite a bit	Extremely	Prefer not to answer	
5	I avoided letting myself get upset when I thought about it or was reminded of it.	Not at all	A little bit	Moderately	Quite a bit	Extremely	Prefer not to answer	
6	I thought about it when I didn't mean to.	Not at all	A little bit	Moderately	Quite a bit	Extremely	Prefer not to answer	
7	I felt as if it hadn't happened or wasn't real.	Not at all	A little bit	Moderately	Quite a bit	Extremely	Prefer not to answer	
8	I stayed away from reminders of it.	Not at all	A little bit	Moderately	Quite a bit	Extremely	Prefer not to answer	
9	Pictures about it popped into my mind.	Not at all	A little bit	Moderately	Quite a bit	Extremely	Prefer not to answer	
10	I was jumpy and easily startled.	Not at all	A little bit	Moderately	Quite a bit	Extremely	Prefer not to answer	
11	I tried not to think about it.	Not at all	A little bit	Moderately	Quite a bit	Extremely	Prefer not to answer	
12	I was aware that I still had a lot of feelings about it, but I didn't deal with them.	Not at all	A little bit	Moderately	Quite a bit	Extremely	Prefer not to answer	
13	My feelings about it were kind of numb.	Not at all	A little bit	Moderately	Quite a bit	Extremely	Prefer not to answer	
14	I found myself acting or feeling like I was back at that time.	Not at all	A little bit	Moderately	Quite a bit	Extremely	Prefer not to answer	
15	I had trouble falling asleep.	Not at all	A little bit	Moderately	Quite a bit	Extremely	Prefer not to answer	
16	I had waves of strong feelings about it.	Not at all	A little bit	Moderately	Quite a bit	Extremely	Prefer not to answer	
17	I tried to remove it from my memory.	Not at all	A little bit	Moderately	Quite a bit	Extremely	Prefer not to answer	
18	I had trouble concentrating.	Not at all	A little bit	Moderately	Quite a bit	Extremely	Prefer not to answer	
19	Reminders of it caused me to have physical reactions, such as sweating, trouble breathing, nausea, or a pounding heart.	Not at all	A little bit	Moderately	Quite a bit	Extremely	Prefer not to answer	
20	I had dreams about it.	Not at all	A little bit	Moderately	Quite a bit	Extremely	Prefer not to answer	
21	I felt watchful and on-guard.	Not at all	A little bit	Moderately	Quite a bit	Extremely	Prefer not to answer	
22	I tried not to talk about it.	Not at all	A little bit	Moderately	Quite a bit	Extremely	Prefer not to answer	
Section 3 (State Trait Anxiety Inventory - 6)								

A number of statements which people have used to describe themselves are given below. Read each statement and then click the most appropriate box to indicate how you feel right now, at this moment. There are no right or wrong answers. Do not spend much time on any one statement but give the answer which seems to describe your present feelings best.
								
1	I feel calm	Not at all	Somewhat	Moderately	Very much	Prefer not to answer		
2	I feel tense	Not at all	Somewhat	Moderately	Very much	Prefer not to answer		
3	I feel upset	Not at all	Somewhat	Moderately	Very much	Prefer not to answer		
4	I am relaxed	Not at all	Somewhat	Moderately	Very much	Prefer not to answer		
5	I feel content	Not at all	Somewhat	Moderately	Very much	Prefer not to answer		
6	I am worried	Not at all	Somewhat	Moderately	Very much	Prefer not to answer		
Section 4 (General health status)								

Please pick the one answer that is right for you.
								
1	In general, would you say your health is:	Excellent	Very good	Good	Fair	Poor	Prefer not to answer	

